In addition to the screening assessment, there will be 30 study visits. The first visit (study start day) will correspond to the 1st varenicline dose and the 1st rTMS session. There will be 4 consecutive weeks of rTMS (20 sessions). Weekly follow-up visits will occur for the 12 weeks of the trial and a final visit will occur at week 26. The TLFB, SAFTEE, concomitant medication log and Adverse Event log will be administered/ updated at every visit. CO measurements will also be taken at every visit. Regular pregnancy testing for females will occur throughout the study. Selective questionnaires (described below in Outcome Measures) will also be administered at study sessions. Urine drug testing will be conducted as required. There will be a total of 4 blood draws (including the screening session). Cotinine blood samples will not be analyzed upon collection. The clinical lab will process the samples and the study staff will pick up the samples and store them in a -20°C freezer. Analysis will be done in batches of 30 or more samples.

*Varenicline Treatment:*

All participants will receive varenicline pharmacotherapy, beginning at Week 1, for a total duration of 3 months (12 weeks). A target quit date for all participants will be set for Day 15. The varenicline dosage schedule will be that standard for smoking cessation. It will consist of 0.5 mg tablet once a day for the first three days (day 1 – day 3), followed by four days of 0.5 mg BID (i.e. twice a day: AM and PM; day 4-7). The target daily dose of 2 mg (1 mg BID, i.e. twice

a day: AM and PM) will begin on Week 2 (day 8) and extend until the end of treatment. Subjects will be advised to orally consume the tablet with food and water. Notably, we may use 1 mg daily if 2 mg daily is not well tolerated. The study medication will be dispensed weekly by the CAMH pharmacy. Compliance will be assessed through reported missed doses at weekly visits (see *Follow-up Visits* section below).

*rTMS:*

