## Data Analysis

Descriptive statistics will be used to compare groups (Sham, rTMS) at baseline on main clinical and demographic variables. Fisher's Exact and Mann-Whitney U test will be used for categorical and continuous variables, respectively. Subjects with missing values in the primary outcome (abstinence at 4, 12 or 26 weeks) will be compared with completers on baseline characteristics, to help in the understanding of the reasons for missing values, if at least 10 subjects (20%) are found to be missing. Mixed effect logistic regression that uses abstinence at 4, 12 and 26 weeks as dependent variables will be adjusted to the data, with groups and categorical time (4, 12 and 26 weeks) specified as fixed effect, and subject intercepts as random effects. Baseline variables correlated with missingness and/or known to be associated with the outcome will be added as covariates with focus on model parsimony (not to include many covariates) due to small sample size. The primary hypothesis will be tested using a contrast that compares abstinence at week 12 in the logit scale. Similarly, abstinence will also be compared at weeks 4 and 26 as part of our secondary objectives. Mixed effect models that uses maximum likelihood estimation accounts for missingness in the dependent variable by using all available information in the estimation, under the MAR assumption (Missing At Random – the values of a data points are not associated with the missing status of the data point after accounting for relevant covariates) [49]. Other measures related to our secondary objectives (e.g., FTND, CO, TLFB, etc.) will also be analyzed using linear mixed or generalized mixed models, depending on the nature of the outcome of interest. Graphs will be used to explore the data, the models assumptions (for example, residual plots), as well as model results (for example, estimated means plot). Due to small sample, effect sizes with 95% confidence intervals as well as standardized effect sizes will be reported.

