### **Termination of the Study**

Reasons for withdrawing individual subjects from the study may include one or more of the following:

- 1) Failure to continue to meet inclusion criteria;
- 2) Severe rTMS side effects;
- 3) Major protocol violation;
- 4) Subject lost to follow-up;
- 5) Withdrawal of consent;
- 6) Pregnancy
- 7) The subject missed more than 3 days of TMS treatment during the treatment trial period (not including holiday closures or due to COVID)

Notably, any subject may be discontinued from the study at the discretion of the Qualified Investigator if it is deemed to be in the best interest of the subject.

When participants are prematurely withdrawn they will be replaced by a new participant until the total recruitment aims are met or until the trial is stopped. Replacement will be according to the inclusion and exclusion criteria above and will follow the same procedure as for the original participants. Data collected until the time of withdrawal may be used in analyses.

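### The primary model takes no account of smoking recorded between Weeks 4 and 12, so a participant abstinent at Week 4 who then relapses and is lost for good is treated as probably abstinent at Week 12

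*Combined protocol and SAP*

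**What the plan says.** The Data Analysis section defines the primary model: "Mixed effect logistic regression that uses abstinence at 4, 12 and 26 weeks as dependent variables will be adjusted to the data". Its terms are arm and visit as fixed effects, plus a random intercept for each participant. On covariates it says: "Baseline variables correlated with missingness and/or known to be associated with the outcome will be added as covariates". On missing outcomes, it says that maximum likelihood "accounts for missingness in the dependent variable by using all available information in the estimation, under the MAR assumption". The test is then specified: "The primary hypothesis will be tested using a contrast that compares abstinence at week 12 in the logit scale".

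Under Total Number of Study Visits, the protocol collects far more smoking data than that: "The TLFB, SAFTEE, concomitant medication log and Adverse Event log will be administered/ updated at every visit", and "CO measurements will also be taken at every visit". Visits are weekly through Week 12, with a last one at Week 26. Data Analysis does use TLFB and CO, but as secondary outcomes in models of their own.

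Termination of the Study leaves the use of data from withdrawn participants open: "Data collected until the time of withdrawal may be used in analyses". The documents contain no rule that counts missing abstinence as smoking, and no sensitivity analysis to the missing-at-random (MAR) assumption.

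**The concern.** MAR is a statement about the data in the model. For someone permanently lost between Weeks 4 and 12, the only post-baseline value in the model is the Week 4 result. If that result was abstinent, the likelihood treats the person much like other Week 4 abstainers who stayed in the trial, even when the TLFB at Week 7 or 8 shows a return to smoking. Loss that follows a recorded relapse is unlikely to be random given Week 4 status. It is much closer to random given the last recorded status, and that status is already in the database.

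At stake is the Week 12 contrast in a trial of about 30 recruits per arm, where a few people classified the wrong way can be seen in the estimate. Because the use of pre-withdrawal data is optional, the choice might also be made after the results are known.

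**Working it through.** **Planned figures.** For 40% v 70%, two-sided 0.05 and 80% power: n = [1.960 × √(2 × 0.55 × 0.45) + 0.842 × √(0.40 × 0.60 + 0.70 × 0.30)]² / 0.30² = (1.379 + 0.565)² / 0.09 ≈ 42 per arm, as the plan states. Recruiting 60 for 50 completers implies a loss of 10/60 = 16.7%, or 5 per arm.

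**Check 1: how the planned type of model treats a lost relapser.** A random-intercept logistic model with separate arm-by-visit means was fitted by maximum likelihood to illustrative data. Both arms had the same 30 participants. The patterns for Weeks 4, 12 and 26 (1 = abstinent) were 111: 8, 110: 3, 011: 1, 100: 5, 000: 13. That gives 16/30 abstinent at Week 4 and 12/30 = 40% at Week 12. Only the 40% and the 30 per arm come from the plan.

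- Three of the five active-arm relapsers (100) become lost after Week 4. Fitted Week 12 abstinence is 47.8% active v 40.3% sham, although the truth is 40% in both. Each lost relapser carries an implied probability of about 0.81. As a check, (12 + 3 × 0.81)/30 = 48.1%.
- In the same fit, a lost participant who was smoking at Week 4 carries only 0.10. Removing three such participants instead gives 40.9% v 40.1%.
- If a Week 4 abstainer misses Week 12 but is seen smoking at Week 26, the probability falls from 0.81 to 0.56.
- If recorded smoking is used, the active arm returns to 12/30 = 40%.

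This shows the mechanism. As a size it is extreme, because every loss is a relapsed Week 4 abstainer in one arm.

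**Check 2: size under a spread of dropout.** All rates here are assumptions. Abstinence at Week 4 is 50%, weekly relapse 6% and weekly quitting 3%. Each week, a fraction d_s of smokers and d_a of abstainers is lost, and then status changes. The eight-week truth is 1/3 + (0.50 − 1/3) × 0.91⁸ = 41.2%. It is 64.7% in Week 4 abstainers and 17.7% in Week 4 smokers. As a stand-in for the mixed model, the estimate is the Week 12 rate among those observed in each Week 4 group, weighted by the size of that group.

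| d_s / d_a per week | Lost, Weeks 4–12 | Observed rate: Week 4 abstainers, smokers | Estimate | Bias (points) |
|---|---|---|---|---|
| 3% / 1% | 15.4% | 66.3%, 18.6% | 42.5% | +1.3 |
| 4% / 1% | 18.8% | 67.1%, 19.2% | 43.1% | +1.9 |
| 6% / 1% | 25.1% | 68.6%, 20.3% | 44.4% | +3.3 |
| 8% / 1% | 30.6% | 70.0%, 21.5% | 45.8% | +4.6 |

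In the 4%/1% row, Week 4 abstainers contribute 0.5 × (67.05 − 64.68) = 1.2 points and Week 4 smokers 0.5 × (19.17 − 17.66) = 0.8. The credit per lost smoker is small, but more of them are lost.

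**Contrast.** With no true effect, 3%/1% in active and 8%/1% in sham give 42.5 − 45.8 = −3.3 points; swapping the arms gives +3.3. With equal dropout and no effect the biases cancel. The standard error at 25 per arm with 40% in each is √(2 × 0.24/25) = 13.9 points, so 3.3 points is 0.24 of a standard error.

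**What the weekly readings recover.** In this set-up loss depends only on the last recorded status, so week-by-week imputation from that status removes the bias by construction. A harder case lets status change before the missed visit, so that the final relapse is unseen. At 4%/1%, conditioning on Week 4 alone then gives 43.7%, and weekly imputation gives 41.9%, against a true 41.2%. Most of the bias goes, but not all of it.

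**The case against.** Some stronger readings are tempting but not supported.

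- A reader might infer that anyone recorded smoking before being lost is credited with abstinence from Week 4 alone. That is too broad. Those smoking at Week 4 receive little credit, those lost before Week 4 have no outcome in the model, and Week 26 informs the fit for anyone who returns. Arm and baseline covariates also enter. Maximum likelihood imputes nothing, so the credit is implicit in the fit.
- A reader might infer that the plan ignores TLFB and CO, or breaks its own promise to use all the information. It analyses both as secondary outcomes, and the sentence on available information describes how likelihood methods handle partly observed outcomes.
- A reader might infer a bias in favour of active rTMS. The direction depends on which arm loses more relapsed participants, and the documents do not say.

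The objection on size also has force. Near the planned loss, the bias in one arm is below one participant (1.9% of 30 = 0.6) and small beside sampling error. The larger figures need more loss than planned, and the higher dropout among smokers is an assumption.

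Finally, a rich imputation model fitted separately in 25 to 30 people per arm would risk separation, and last status before loss has no natural value in completers. Both points stand and shape the remedy. What remains is that relapse observed in Weeks 5 to 11 has no route into the primary contrast.

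**Conclusion.** The point holds in a limited form and is a cheap improvement, not a flaw that invalidates the analysis. As written, the primary model treats a Week 4 abstainer who is recorded smoking in Weeks 5 to 11 and never returns as probably abstinent at Week 12. MAR given only the modelled data is therefore doubtful, although the readings that would make it more credible are collected.

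Under the assumed rates the overstatement is about 1 to 2 points per arm near the planned loss of about 17%, and 3 to 5 points at 25% to 31%. The planned figure covers the whole trial, so any part of it that falls before Week 4 reduces this bias. For the contrast the error can go either way, and it cancels if there is no effect and the arms lose participants alike. These sizes rest on assumed relapse, quitting and dropout rates and, in Check 2, on a simplified estimator.

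**What to change.** 1. Pre-specify multiple imputation of missing Week 12 status from a small model: arm and 7-day TLFB status at the last attended visit. Fit it on participants with Week 12 observed, using their TLFB status at the same study week. Sequential weekly imputation does this and gives completers a defined predictor.
2. Add CO or Week 4 status only if the model stays stable, and use penalised or Bayesian fitting if there is separation. If CO is used, define how it enters; the documents give no CO cut-off for abstinence.
3. Report this beside the three-visit mixed model and state in advance which of the two is primary.
4. Add a sensitivity analysis in which missing Week 12 status counts as smoking.
5. In Termination of the Study, replace the permissive wording with a commitment that readings collected before withdrawal will be used, subject to the terms of any withdrawal of consent.

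The cost is SAP wording and modest programming, with no new data. There are limits. The TLFB status is self-report without cotinine, and the imputation model must stay small at about 30 per arm. For those lost before the Day 15 quit date, recorded smoking is expected and adds little.

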## Aims and Hypotheses

### *Hypotheses:*

Primary: Active deep rTMS intervention will improve point prevalence abstinence rates at the end of varenicline treatment (Week 12) as measured by self-report and confirmed with plasma cotinine levels.

Secondary 1: Active deep rTMS intervention will significantly attenuate craving and reduce cigarette consumption and dependence severity.

Secondary 2: Active deep rTMS intervention will significantly improve short-term point prevalence abstinence rates and long-term prolonged and continuous abstinence rates.

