## Sample Size and Power Calculation

Based on the results of a recently completed multi-centre trial [4] and results from our previous trial investigating varenicline's efficacy in patients in a residential drug program, we anticipate a 12 week abstinence point prevalence rate of approximately 40% following treatment with varenicline. To detect a clinically relevant 30% difference in the proportion of abstinence between active deep rTMS and sham rTMS treatments with a power of 0.80 ( $\alpha = 0.05$ ), we would need  $n=42$  participants per study arm. However, in light of the pilot nature of this proposed study and the allotted time frame for study completion, we will recruit  $n=25$  participants per study arm (power = 0.66). However, we anticipate attrition with this study sample and as such, we will recruit  $n=30$  per arm to obtain 50 completers in total.

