## Outcome Measures

Main Outcome Measure: 7-day point prevalence abstinence at the end of 12 weeks. This outcome will be measured by self-report of abstinence for the past 7 days, and confirmed using a plasma cotinine measurement of  $\leq 15$  ng/ml

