## Secondary Outcome Measures:

1) Fagerstrom Test of Nicotine Dependence (FTND). The FTND will be used to assess physical

dependence severity in participants [40].

2) Expired Carbon Monoxide (CO) Measurements. Expired CO measurements will be regularly taken as a biological confirmation of recent smoking.

3) Cigarettes per day. The Timeline Follow-Back (TLFB) will be used to determine daily self-reported cigarette consumption [42].

4) Minnesota Nicotine Withdrawal Scale (MNWS). The MNWS will be used to assess tobacco withdrawal symptoms [50].

5) Tiffany Questionnaire of Smoking Urges (T-QSU). The T-QSU will be used to assess symptoms of craving/urges for tobacco [51].

6) Point prevalence abstinence at end of 4 weeks: This outcome will be measured by self-report of abstinence for the past 7 days and confirmed using a plasma cotinine measurement of <15 ng/ml.

7) Prolonged abstinence from end of treatment (Week 12) to end of follow up (Week 26). This outcome will be measured by self-report of continuous abstinence since the last visit (at Week 12) and confirmed using a plasma measurement of <15 ng/ml.

8) Prolonged abstinence with 2-week grace period at end of follow up (Week 26). This outcome will be measured by self-report of continuous abstinence since Week 4 and confirmed using a plasma measurement of <15 ng/ml.

9) Continuous abstinence at 6 months: This outcome will be measured by self-report of continuous abstinence since the target quit day (Week 2) and confirmed using a plasma measurement of <15 ng/ml.

The FTND, T-QSU and MNWS will be administered weekly for the first month (i.e. 4 weeks) and subsequently at 8, 12 and 26 weeks.

In the case that a participant declines blood draws, urine will be collected instead for the quantification of cotinine levels.

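### The primary mixed logistic model lists no group-by-time term, so its promised week-4, week-12 and week-26 contrasts are one pooled effect

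*Combined protocol and SAP*

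**What the plan says.** The Data Analysis section fits one mixed effect logistic regression to abstinence at three visits, "with groups and categorical time (4, 12 and 26 weeks) specified as fixed effect, and subject intercepts as random effects". The only further terms it allows are a small number of baseline covariates. It then states: "The primary hypothesis will be tested using a contrast that compares abstinence at week 12 in the logit scale". And next: "Similarly, abstinence will also be compared at weeks 4 and 26 as part of our secondary objectives". Neither this section nor any other names a group-by-time term.

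Elsewhere the target is week 12 alone. The Outcome Measures section reads "Main Outcome Measure: 7-day point prevalence abstinence at the end of 12 weeks", and the sample size section builds its effect on that visit: "we anticipate a 12 week abstinence point prevalence rate of approximately 40% following treatment with varenicline". One phrase in Data Analysis points the other way. The sentence on missing data begins "Subjects with missing values in the primary outcome (abstinence at 4, 12 or 26 weeks", as if all three visits made up the primary outcome.

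At week 26 the Secondary Outcome Measures list only prolonged and continuous abstinence, the first being "Prolonged abstinence from end of treatment (Week 12) to end of follow up (Week 26". Data Analysis does not say which definition of week-26 abstinence enters the model.

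**The concern.** A model with group and time as main effects has a single group effect, shared by all visits. It cannot give three different comparisons. If an analyst follows the listed terms, the primary test answers whether active rTMS helps on average over weeks 4, 12 and 26, which is not the declared question.

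The two questions coincide only if the odds ratio is the same at all three visits. The plan gives no basis for that. Stimulation stops at week 4, varenicline stops at week 12, and week 26 is off both. If the effect varies, an early effect can make week 12 look positive, or null visits can dilute a real week-12 effect. Leaving the term open also lets two analysts fit different primary models and both claim to follow the plan, and the choice could be made after the data are seen.

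**Working it through.** **1. Algebra (no assumptions).** As listed, for participant *i* at visit *t*: logit P = a + b·group + time_t + u_i. Active minus sham at visit *t* is (a + b + time_t + u_i) − (a + time_t + u_i) = b, for t = 4, 12 and 26 alike: one estimate, one standard error, one p-value. Baseline covariates do not change this. With an interaction the contrast is b + g_t (g_4 = 0), so week 12 is b + g_12. That takes two more parameters.

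**2. The plan's own figure.** Inputs from the sample size section: 40% sham, a 30% difference read as 40% vs 70%, alpha 0.05 (two-sided assumed), power 0.80.

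n = [1.96·√(2·0.55·0.45) + 0.8416·√(0.40·0.60 + 0.70·0.30)]² / 0.30² = (1.379 + 0.565)² / 0.09 ≈ 42 per arm, as stated. This is a single-visit calculation at week 12. (The same formula gives power 0.57 at 25 per arm, not the stated 0.66; that is a separate matter and nothing below rests on it.)

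**3. Large-sample check.** 25 per arm. Assumed: sham 40/40/30% at weeks 4/12/26, random-intercept SD 1 to 3. Power = Φ(estimate/SE − 1.96).

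- Effect at week 12 only (40% vs 70%). With SD 1 the true week-12 log odds ratio is 1.51. The listed model gives 0.51 (SE 0.46), close to 1.51/3: Φ(0.51/0.46 − 1.96) = 0.20. With the interaction: Φ(1.51/0.73 − 1.96) = 0.54. Over SD 1 to 3, power is 0.16–0.20 against 0.52–0.54.
- Effect at week 4 only. The listed model reports the same 0.51–0.91 as its week-12 log odds ratio and rejects in favour of active in 16–20%. The interaction model gives 0 and the nominal 2.5%.
- Effect at weeks 4 and 12, gone by week 26. The listed log odds ratio is 1.02–1.71 against a true week-12 value of 1.51–2.70; power is 0.41–0.58 against 0.51–0.54.
- Constant effect (sham 40% at every visit). Power is 0.65–0.85 listed, 0.51–0.54 with the interaction.

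**4. Simulation.** 25 per arm, 40% sham at week 12 and a 30-point effect come from the plan. Assumed: sham 40% at week 4; latent within-subject correlation 0.5, 0.7 or 0.85; no missing data. Week 26 was run two ways: (A) point prevalence, sham 25% or 40%; (B) prolonged, success requiring week-12 abstinence, sham 15% or 25%. That makes 3 × 4 = 12 sets. Each cell has 1,000 replicates (Monte Carlo SE at most 1.6 points), with maximum likelihood fits tested at two-sided 0.05. The table shows the percentage of trials in which the week-12 test rejects, as the range over the 12 sets:

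| Effect pattern | LR test, listed | LR test, interaction | Wald, listed | Wald, interaction |
|---|---|---|---|---|
| None | 4.2–6.9 | 4.7–7.0 | 1.7–5.8 | 1.2–4.9 |
| Week 4 only | 15–21 | 4.2–6.5 | 8–18 | 0.6–4.6 |
| Week 12 only | 14–22 | 56–61 | 10–19 | 27–52 |
| Weeks 12 and 26 only | 37–51 | 57–64 | 30–48 | 31–53 |
| Constant +30 points | 70–83 | 59–63 | 49–81 | 33–54 |
| Fade +30, +15, 0 | 27–34 | 18–22 | 17–32 | 5–16 |

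In the week-4-only row the week-12 rates are equal, so every rejection is false. There the listed model's odds ratio tends to 1.8–3.4 (A) or 2.3–4.4 (B). Under the fade it is 0.87–1.17 times the week-12 value.

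Smaller repeat simulations at one setting (reading A, correlation 0.7, sham 25% at week 26, likelihood-ratio test; 300 and 250 replicates) agreed within simulation error. For an effect at week 12 only they gave 16% vs 62% and 20% vs 59%, against 18.5% vs 61.2% in the main run.

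**The case against.** The strongest reply is that the interaction is implied. Separate contrasts at three visits would be empty without it, and the aims and hypotheses set week 12 apart from weeks 4 and 26. The phrase that calls all three visits the primary outcome sits in a sentence about missing data and does not define the test. This is persuasive about intent. It does not supply the term: the model's fixed effects are written out, and the instruction to keep covariates few does not encourage an analyst to add more.

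A second reply is that the large differences come from effects confined to one visit. That is true, and such patterns are extremes. With a constant effect pooling is valid and stronger. With a smooth fade, natural enough when stimulation stops at week 4, the pooled odds ratio lies near the week-12 value. The simulations also omit attrition, which the plan expects, and do not cover the week-26 definitions that require abstinence since week 2 or week 4. The ranges are therefore illustrations. The algebra in step 1 depends on none of this.

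Third, adding the interaction does not settle everything. The table shows that the choice between Wald and likelihood-ratio tests also matters at this sample size. That stands and is taken into the fix.

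**Conclusion.** The concern holds. As written, the primary model cannot give the week-12 comparison that the plan makes primary; it gives one pooled odds ratio for all three visits. That follows from the listed terms alone.

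How much it matters depends on an unknown time pattern and on the assumed sham rates and correlations. By likelihood-ratio test, false rejection at week 12 rises to 15–21% if the effect is at week 4 only, and power falls to 14–22% from 56–61% if it is at week 12 only. With a delayed effect at weeks 12 and 26 the loss is smaller (37–51% against 57–64%) and nearly vanishes under Wald. With no effect at any visit both models stay near or below the nominal level. This should be fixed before unblinding. It is a specification error with a simple remedy and does not undermine the design.

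**What to change.** State the fixed effects as *group, categorical time and group-by-time interaction*. Define the primary test as the active-minus-sham contrast at week 12 from that model, with separate contrasts at weeks 4 and 26. Name the test statistic in advance: under no effect the Wald version rejects in only 1.2–4.9%, the likelihood-ratio version in 4.7–7.0%. Reword the missing-data sentence so that only week 12 is called primary, and say which definition of week-26 abstinence enters the model.

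The change is one phrase plus two model parameters, with no effect on the stated sample size, the visits or the procedures. The real cost is power where pooling would have helped. With a constant effect it is 59–63% instead of 70–83% (likelihood-ratio) or 33–54% instead of 49–81% (Wald). With the fade it is 18–22% instead of 27–34% (likelihood-ratio). The plan already states only 0.66 power, so this is not trivial. If the sponsor prefers the pooled effect for that reason, it should declare a common effect over the three visits as the primary target and drop the claim to a week-12 test.

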### *Aims:*

Primary: To examine the efficacy of bilateral deep repeated transcranial magnetic stimulation (rTMS; 10 Hz) directed to the insular cortex, relative to sham stimulation, on point prevalence smoking abstinence in smokers who are receiving standard varenicline treatment (2 mg/day).

Secondary 1: To examine the effect of bilateral deep rTMS directed to the insular cortex, relative to sham, on other smoking outcomes throughout study duration including self-reported craving, cigarette smoking and dependence severity.

Secondary 2: To examine the effect of bilateral deep rTMS directed to the insular cortex, relative to sham, on abstinence at the end of rTMS treatment (point-prevalence abstinence at Week 4) and at 6-month follow-up (prolonged and continuous abstinence at Week 26).

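### Smoking recorded before Week 26 already settles abstinence outcomes 8 and 9 as failures, but the plan has no rule for this and leaves a missed Week 26 to a missing-at-random model

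*Combined protocol and SAP*

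**What the plan says.** - **Endpoints.** The second secondary aim names its long-term endpoints as "6-month follow-up (prolonged and continuous abstinence at Week 26". Under Secondary Outcome Measures, outcome 9 reads "This outcome will be measured by self-report of continuous abstinence since the target quit day (Week 2", with cotinine confirmation. Outcome 8 counts from Week 4 and outcome 7 from Week 12, both to Week 26.
- **Data collected.** Under Total Number of Study Visits: "The TLFB, SAFTEE, concomitant medication log and Adverse Event log will be administered/ updated at every visit". Visits are weekly to the end of the 12 weeks, followed by a single visit at Week 26.
- **Main model.** Data Analysis specifies "Mixed effect logistic regression that uses abstinence at 4, 12 and 26 weeks as dependent variables", with group and categorical time as fixed effects and a subject random intercept. It adds that "abstinence will also be compared at weeks 4 and 26 as part of our secondary objectives".
- **Missing data.** The stated handling is "Mixed effect models that uses maximum likelihood estimation accounts for missingness in the dependent variable by using all available information in the estimation". The plan makes this conditional on MAR. If at least 10 subjects are missing, they are compared with completers at baseline. No rule counts missing as smoking, and no sensitivity analysis departs from MAR.
- **Other measures.** Further secondary measures "will also be analyzed using linear mixed or generalized mixed models, depending on the nature of the outcome of interest".
- **Withdrawals.** Termination of the Study permits the use of data collected before withdrawal but does not require it.

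**The concern.** Outcomes 8 and 9 are all-or-nothing over a window. A participant whose TLFB shows smoking at Week 8 has failed both, and nothing at Week 26 can change that. The plan nevertheless defines these outcomes through self-report and cotinine at Week 26 and treats an absent Week 26 value as unknown. Following it literally, the analyst estimates a value that the trial already holds.

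The joint model does not fully repair this, for three reasons:

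1. It contains abstinence at Weeks 4, 12 and 26 plus a few baseline covariates. Lapses in Week 3 and Weeks 5 to 11 are recorded but not in it. If absence depends on those lapses, MAR fails given what the model sees, although the trial has the information.
2. It gives a positive probability to an impossible result. A Week 12 smoker cannot be continuously abstinent since the quit day.
3. The plan does not say which Week 26 definition enters the model. A definition left out would fall under the general sentence on other measures. It would then be one binary value per person, with no repeated measure to support the likelihood argument.

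At stake are the long-term abstinence rates behind the second secondary hypothesis. The definition of the primary Week 12 outcome is not in question.

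**Working it through.** **Inputs.** The plan gives no Week 26 abstinence rate and no Week 26 missingness, so there is no figure of its own to reproduce on this point. The nearest are the attrition allowance (60 recruited for 50 completers, 10/60 = 16.7%), the missingness trigger (10/50 = 20%) and the anticipated Week 12 rate of 40%. Everything about Week 26 below is an assumption.

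**Step 1. Hand arithmetic, attenders only.** Take 25 per arm, 5 true successes (5/25 = 20%) and 5 known failures absent. The attenders' rate is 5/20 = 25%, which is 5 points too high. Coding the 5 as failures restores 5/25 = 20%. With 3 successes and 3 absent failures the error is 3/22 − 3/25 = +1.6 points; with 7 and 8 it is 7/17 − 7/25 = +13.2 points.

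**Step 2. The planned model.** Weekly smoking status in Weeks 3 to 12, then relapse to Week 26, was simulated for 200,000 participants per setting. The random-intercept logistic model for Weeks 4, 12 and 26 was fitted by maximum likelihood. Week 12 abstinence was about 42%. True Week 26 rates were about 18% (outcome 9) and 22% (outcome 8). The probability of absence was 25% vs 5%, 35% vs 10% or 50% vs 5% for those with and without the feature in the first column, giving 17% to 37% missing overall. Entries are bias in percentage points across both outcomes.

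| Absence depends on | Attenders only | Joint model, Week 26 left missing | Joint model, recorded smoking coded as failure |
|---|---|---|---|
| Week 12 status | +2.6 to +8.0 | +0.4 to +1.2 | −0.4 to +0.1 |
| Lapse in Weeks 5–11 | +3.2 to +10.9 | +0.9 to +3.1 | −0.4 to +0.1 |
| Same, Week 12 also missed | +3.2 to +10.8 | +1.5 to +4.1 | −0.7 to −0.1 |
| Relapse after Week 12 | +2.9 to +9.7 | +1.4 to +4.4 | +0.5 to +2.4 |

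At the lowest absence level (17% to 19% missing, near the plan's own 16.7%) the joint-model bias is +0.4 to +1.9 points. Between 83% and 97% of those absent already had smoking on record. The last column assumes complete weekly records through Week 12; missed weekly visits would leave more unresolved. The last row keeps a residual bias because relapse after Week 12 is not recorded before Week 26.

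**Step 3. Absence unrelated to smoking.** With 20% missing, the joint model shows no upward bias (0.221 against a true 0.223; 0.255 against 0.255). Coding known failures and leaving the rest missing then gives 0.210 in the model, and 0.191 as a simple proportion, against 0.223. All recorded failures are now counted while some possible successes are still absent, so failures are over-represented.

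**Step 4. Arm contrast.** If only failures are absent, with probability m, the attenders' rate is p / (p + (1 − p)(1 − m)).

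- Absence differs by arm: true 15% in both arms, m = 0.30 (sham) and 0.15 (active). This gives 0.15/0.745 = 20.1% and 0.15/0.8725 = 17.2%, a spurious −2.9 points. Swapping the arms reverses the sign.
- Equal absence: m = 0.20, true 15% and 30%. This gives 18.1% and 34.9%, so a 15.0-point difference reads 16.8. The odds ratio, the planned scale, stays at (0.30/0.70)/(0.15/0.85) = 2.43 because (1 − m) cancels.

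**The case against.** The strongest reply is that the plan does not drop anyone. A participant absent at Week 26 keeps the Week 4 and Week 12 results in the likelihood, and the general sentence on other measures gives FTND, CO and TLFB as its examples, not abstinence. That stands. A reader might infer that the analysis is one of Week 26 attenders, or that known failures are set to missing by instruction. The documents say neither. They are silent on the derivation, and the attenders-only figures apply only if an outcome is modelled alone.

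Several further points also stand:

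- Upward bias is not automatic; it needs absence linked to smoking (Step 3).
- Outcome 7 hardly belongs here. No visit falls between the end of treatment and Week 26, so almost nothing recorded earlier can settle it.
- A cotinine sample taken at the end of Week 4 reflects smoking before outcome 8's window opens, so it cannot be used as a failure on that outcome.
- Making missing-equals-smoking the main rule, or abandoning the mixed model, would exchange one untestable assumption for another. In the Step 2 settings, missing-equals-smoking understates the true rate by 0.9 to 2.3 points.
- The bias is small beside the sampling error. At 15% vs 30% with 25 per arm, the 95% half-width is 1.96 × √(0.15 × 0.85/25 + 0.30 × 0.70/25), about 23 points.

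None of this supplies the missing rule. A confidence interval does not reflect this bias, and one participant in 25 is 4 points, so a few cases decided late can visibly move a reported rate.

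**Conclusion.** The point holds for outcomes 8 and 9 and should be fixed. The plan collects data that logically settle these outcomes, gives no rule for using them when Week 26 is missed, and relies on a MAR model that omits most of the weekly smoking record. Where absence is related to smoking, the rates are overstated by roughly 0.4 to 4.4 points in the joint model and by 2.6 to 10.9 points in an attenders-only analysis. The sizes depend on the assumed Week 26 rates and on 17% to 37% missing; the logical gap does not.

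A reader might go further and conclude that the treatment comparison is biased in favour of one arm. The documents do not support this: nothing in them suggests that absence after smoking would differ by arm, and if it did, the direction could be either way.

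**What to change.** In Data Analysis, with a cross-reference from outcomes 8 and 9:

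1. Code as not abstinent any randomised participant with smoking recorded on TLFB inside the window (after the target quit date for outcome 9, after Week 4 for outcome 8) or with a positive Week 12 cotinine. Apply this whether or not Week 26 is attended, and include participants withdrawn early.
2. State that a Week 4 cotinine result does not count as failure on outcome 8.
3. Keep as missing only those with no recorded smoking and no Week 26 visit, and state their rule. One option is MAR conditional on no recorded smoking: multiply the proportion with no recorded smoking by the abstinence rate among those of them who attended.
4. Add a sensitivity analysis that counts these remaining cases as smoking.
5. Name which Week 26 definition enters the joint model, and how the others are analysed.

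The cost is SAP wording and a derivation from data already collected. Reported long-term rates will be somewhat lower. Item 3 cannot be skipped, because coding known failures alone can push rates slightly too low (0.210 against 0.223 in Step 3). The rules should be fixed before unblinding.
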